
Purpose/Objectives: Primary Aims
 
1: Evaluate the safety of high-dose spironolactone in combination of Patiromer in acute decompensated heart failure patients.
 
2: Evaluate the efficacy of high-dose spironolactone in combination of Patiromer in causing volume loss and symptom relief in patients with ADHF treated with high-dose spironolactone.
 
Secondary Aims
 
1: Evaluate the effect of high-dose spironolactone on urinary sodium excretion and renal function.
 
Research Design/Plan: We propose a prospective exploratory single-arm, open-label pilot study to assess the safety and efficacy of high dose spironolactone in combination with Patiromer in patients hospitalized with decompensation of chronic heart failure who shows sign of resistance of loop diuretics. Patients admitted with decompensated heart failure will be identified from the inpatient cardiology and internal medicine services.
 
Methods: Study Protocol
 
Pre-screening: Patients meeting the inclusion and exclusion criteria will be approached to participate in the study. Informed consent will be taken at this time. These patients will receive intravenous loop diuretic per the discretion of treating physician and will be closely followed for weight loss and symptoms relief.
 
Screening: The patients who don't respond as measured by symptoms relief or <0.5 kg weight loss/day
 
a) Despite furosemide \geq 160 mg IV total daily dose or equivalent dose of torsemide or bumetanide. (1 mg bumetanide = 10 mg torsemide = 20 mg furosemide). ORb) After 48 hours of admission irrespective of diuretic dose. 
will be considered for the study intervention. Patients who have not participated in the pre-screening phase and do not respond adequately to furosemide >160 mg iv daily dose will directly be enrolled into active intervention part of the study.
 
Intervention (High-Dose Spironolactone + Patiromer): Patients will be initiated on spironolactone 100 mg orally once daily along with patiromer 8.4 gm orally (if serum K >4.3 meq/L). The dose of loop diuretic will stay same during rest of the study period. On day 2, the dose of spironolactone will be titrated to 200 mg orally once a day depending on the diuretic response and lab results. Serum potassium and magnesium will be monitored twice a day. An EKG will be performed any time electrolytes are out of range. The dose of patiromer will be increased to 16.8 gm in patients with potassium levels exceeding 5.5 meq/L; or it will be held for serum K <4.3 mEq/L. Treatment will continue till patients achieve euvoolemia or get discharged. Euvoolemia is defined as resolution of symptoms and signs of volume overload.
 
Treatment Failures: Patients will be considered high dose spironolactone failure if they do not achieve a net negative body weight after a minimum of 5 days. High-dose spironolactone may be stopped anytime per the discretion of the treating physician. The patients that do not respond to high-dose spironolactone are considered treatment failures and will be included in the primary endpoint analysis.
 
Concomitant Medications/diet: Patient taking concomitant heart failure medications such as ACEi, ARB and/or beta-blockers are to be continued throughout the study as tolerated. If these medications have not been administered at the time of randomization, timing and sequence of the starting ACEi, ARB or beta-blockers will be left to the discretion of the treating physician. All the patients will be prescribed low Na (<1.5gm/day) and low potassium (50-75 mEq/day) diet.
 
Clinical Relevance: Insert response here
	

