Intervention (High-Dose Spironolactone + Patiromer): Patients will be initiated on spironolactone 100 mg orally once daily along with patiromer 8.4 gm orally (if serum K >4.3 meq/L). The dose of loop diuretic will stay same during rest of the study period. On day 2, the dose of spironolactone will be titrated to 200 mg orally once a day depending on the diuretic response and lab results. Serum potassium and magnesium will be monitored twice a day. An EKG will be performed any time electrolytes are out of range. The dose of patiromer will be increased to 16.8 gm in patients with potassium levels exceeding 5.5 meq/L; or it will be held for serum K <4.3 mEq/L. Treatment will continue till patients achieve euvoolemia or get discharged. Euvoolemia is defined as resolution of symptoms and signs of volume overload.

Patients will be followed till achievement of euvoolemia or discharge. Daily assessment will be done for symptoms, and signs of volume overload including shortness of breath, orthopnea, paroxysmal nocturnal dyspnea, abdominal bloating, lower extremity edema, JVD, and body weight changes. Serum chemistry will be assessed twice a day and urine electrolytes once a day. Neurohormonal analysis will be done at the pre-screening, and at the end of the study duration.

Primary Safety measures:

- 1) Incidence of hyperkalemia as defined by serum K >5.5 meq/day.
- 2) Incidence of hypokalemia as defined by serum <3.5 meq/day
- 3) Renal function: assessed by daily serum creatinine

Primary Efficacy measures:

- 1) Weight loss: using same calibrated scale every day in hospital gown.
- 2) Symptom relief: assessed using a 5-point Likert scale describing magnitude of shortness of breath while the patient is in the supine position.

Secondary Efficacy measures:

	
 1) Urine sodium excretion: assessed by FENa% 2) Urine Sodium/Potassium ratio as a biomarker of aldosterone activity

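### Follow-up ends at euvolemia, which includes symptom resolution, yet symptom relief is a primary efficacy measure with no fixed time point or summary

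*Combined protocol and SAP*

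**What the plan says.** Item 6 (Intervention) gives the same end point to treatment and to observation: "Treatment will continue till patients achieve euvoolemia or get discharged", and "Patients will be followed till achievement of euvoolemia or discharge". The stopping event is defined there too: "Euvoolemia is defined as resolution of symptoms and signs of volume overload".

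Up to that point scoring is daily: "Daily assessment will be done for symptoms, and signs of volume overload including shortness of breath, orthopnea, paroxysmal nocturnal dyspnea", followed by further symptoms, signs and body weight. The second primary efficacy measure is "Symptom relief: assessed using a 5-point Likert scale describing magnitude of shortness of breath while the patient is in the supine position".

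The opening summary (Treatment Failures) adds another route off treatment: "High-dose spironolactone may be stopped anytime per the discretion of the treating physician". Failure is judged on weight alone: "Patients will be considered high dose spironolactone failure if they do not achieve a net negative body weight after a minimum of 5 days". Such patients "are considered treatment failures and will be included in the primary endpoint analysis", but no day or value is attached.

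The Data Analysis Plan deals only with weight loss. Neither the summary nor Item 6 gives an analysis day for the symptom score, a summary measure, a score after the stop, or a rule for patients without one. The design is single-arm and open-label.

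**The concern.** The event that can end a patient's record contains the outcome being measured. Following the plan as written leaves no symptom scores after euvolemia, so this is more than missing analysis detail.

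Two summaries come naturally from such data, and they err in opposite directions. The last available score catches patients who stop for euvolemia at a good moment. The mean by study day loses those same patients, so later days are weighted towards patients who still have symptoms or signs.

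A concurrent control arm under the same rule would share much of this distortion; a single-arm study has none. The pilot is meant to inform a larger randomized trial. A symptom estimate that mixes treatment response with the stop rule and length of stay would be a weak basis for planning that endpoint.

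**Working it through.** **The plan's own figure.** The only statistical figure is 90% power for a weight loss of 2 kg (SD 1.3 kg), two-sided 5%, 20 subjects. A two-sample t-test with 10 per group has noncentrality (2/1.3)/√(1/10 + 1/10) = 3.44 and power 0.902. The figure therefore reproduces as a two-group comparison; a one-sample test on 20 gives more than 0.9999. That mismatch is a separate matter. No figure is stated for the symptom measure.

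**What follows from the text alone.**
1. Observation ends at euvolemia or at discharge.
2. Euvolemia requires symptoms and signs to have cleared, and shortness of breath is among the daily items. A patient who stops for euvolemia has just been judged free of breathlessness. I assume that the Likert score agrees with that judgement; the plan does not link the two.
3. Let *e* be the share who stop for euvolemia and *r* the share with a relieved last score among the rest. The share relieved by last score is *e* + (1 − *e*)·*r*, which is never below *e*, whether or not relief would have lasted another day. The documents give neither *e* nor *r*.
4. On a late day, the patients with a score are those neither euvolemic nor discharged. Removing euvolemic patients, who score well, worsens the mean. The effect is diluted by patients who breathe well but still have, say, edema.

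**Illustration on assumed inputs.** None of these comes from the documents: a 1–5 score with higher worse, patient means 3.5 (SD 0.7), daily noise SD 0.8, entry score at least 3, no discharges, and a stop on the first day the score is at or below a cut-off. The signs requirement is left out, so stopping is easier than under the plan. Results at day 7:

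| True change | Cut-off | Relieved, last score | Relieved, fixed day in all | Mean, still followed | Mean, all |
|---|---|---|---|---|---|
| none | 1 | 9.6% | 1.8% | 3.68 | 3.61 |
| none | 2 | 46.8% | 13.2% | 3.92 | 3.60 |
| 0.2 points/day better | 1 | 44.2% | 23.4% | 2.53 | 2.29 |
| 0.2 points/day better | 2 | 85.7% | 59.9% | 2.95 | 2.29 |

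The last score overstates the share relieved in every row. The mean among those still followed is worse than the full-cohort mean by 3.68 − 3.61 = 0.07 up to 2.95 − 2.29 = 0.66 points.

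Two limits show up in the same runs:
- For mean change, as opposed to share relieved, the last score was the more favourable in 11 of 12 settings (days 5, 7 and 10). The exception was day 10, cut-off 2, with true improvement: −1.93 by last score against −2.03 at the fixed day. Stopping early cuts off later improvement.
- With no true change, the fixed-day mean change is still −0.21, because entry required a poor score. At day 7 the last-score change is −0.36 (cut-off 1) or −0.78 (cut-off 2). A fixed day removes the part due to the stop rule, not regression to the mean at entry.

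A cruder calculation, with an independent 10% chance of resolution each day, gives 1 − 0.9³ = 27%, 1 − 0.9⁵ = 41% and 1 − 0.9⁷ = 52% by last score at days 3, 5 and 7, against 10% on any fixed day. It ignores both the signs requirement and correlation within patients. It is an upper-end illustration and the conclusion does not rest on it.

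**The case against.** The strongest reply is that the plan proposes neither a last-score nor a by-day analysis, so the criticism is of summaries it never states. That is true of the analysis. It does not answer the follow-up rule, which is stated and which removes the scores an undistorted summary would need.

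Several stronger readings are tempting, and the documents do not support them:
- *Every last score is favourable by construction.* Discharge also ends follow-up, and the physician may stop the drug at any time. The statement holds only for patients who stop for euvolemia.
- *Later-day means contain only patients without relief.* Signs must clear as well, so a patient whose breathing is easy but whose edema or JVD persists stays in and contributes good scores.
- *One good day ends the record.* No one-day rule is written. Inclusion requires at least one sign, so a chance good breathlessness score does not stop follow-up while a sign persists.
- *The result reflects the stop rule rather than the drug and is useless for the next trial.* Reaching euvolemia is itself a response that treatment may affect, and the plan's only sizing is on weight. In a single-arm study with continued loop diuretic, a fixed-day score would not isolate the drug effect either.

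It also stands that the size cannot be derived from the documents, and that a discharge-day score is again a score taken at an outcome-related exit.

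**Conclusion.** The concern holds in limited form. Observation ends at euvolemia or discharge, euvolemia includes symptom resolution, and a primary symptom measure has no fixed time point or summary. For patients who stop for euvolemia, the last score is favourable because of the rule; later-day means over-represent patients not yet euvolemic.

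The direction follows from the stop rule: upward for the share relieved by last score, and towards worse scores for later-day means. It assumes that the Likert score agrees with the bedside judgement of euvolemia, and that discharges without euvolemia do not offset the effect. For mean change by last score the direction is usual but not certain. The amount is unknown. In the illustration the day-7 excess in share relieved ran from 9.6 − 1.8 = 7.8 to 46.8 − 13.2 = 33.6 percentage points, with signs ignored. This affects one of two primary efficacy measures in an exploratory pilot. It should be corrected, but it does not undermine the study as a whole.

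**What to change.** Leave the treatment stop rule as it is and change only measurement and analysis:

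1. Continue the daily Likert score to one prespecified day after the first spironolactone dose, for everyone still in hospital, including those already judged euvolemic.
2. Make the primary symptom analysis the change from the last pre-dose score to that day. Choose and justify the day with regard to the day-2 titration step and the protocol's own 5-day minimum for judging failure. A later day leaves more time after titration but meets more early discharges.
3. For patients discharged earlier, use the discharge-day score and report how many there are. Add a sensitivity analysis that counts discharge without euvolemia as not relieved.
4. Report attainment of euvolemia separately, as a cumulative incidence by day with discharge without euvolemia as a competing event.

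The cost is a few extra Likert scores in early responders still in hospital, plus analysis wording. Some dependence on length of stay remains for early discharges, and the report should say so. It should also say that a single-arm change score includes regression to the mean and the effect of continued loop diuretic.

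### A low K >5.5 rate alone cannot show that potassium stayed controlled on the regimen, because a patient whose spironolactone or ACEi/ARB is cut for potassium at or below 5.5 counts as event-free

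*Combined protocol and SAP*

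**What the plan says.** The primary safety measures in Item 6 are "Incidence of hyperkalemia as defined by serum K >5.5 meq/day", hypokalemia below 3.5 in the same printed unit, and daily serum creatinine. The per-day unit is a clerical slip for mEq/L.

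The combined protocol and SAP says the following about what can be changed during treatment:

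- **Spironolactone dose.** It starts at 100 mg. On day 2, "the dose of spironolactone will be titrated to 200 mg orally once a day depending on the diuretic response and lab results" (Item 6, Intervention). No potassium cut-off is attached.
- **Stopping spironolactone.** "High-dose spironolactone may be stopped anytime per the discretion of the treating physician" (Treatment Failures). Again there is no potassium threshold.
- **ACEi, ARB and beta-blockers.** These "are to be continued throughout the study as tolerated" (Concomitant Medications/diet).
- **Patiromer.** 8.4 g if K is above 4.3, 16.8 g if K exceeds 5.5, held below 4.3 (Item 6, Intervention).
- **Fixed elements.** "The dose of loop diuretic will stay same during rest of the study period", and all patients are prescribed a "low potassium (50-75 mEq/day) diet".

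Patients fail treatment "if they do not achieve a net negative body weight after a minimum of 5 days". Those who do not respond "are considered treatment failures and will be included in the primary endpoint analysis". Follow-up runs to euvolemia or discharge, with serum chemistry twice a day.

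**The concern.** Primary Aim 1 is the safety of high-dose spironolactone given with patiromer. Item 4 presents hyperkalemia, particularly alongside an ACEi or ARB, as the chief difficulty with spironolactone and the leading cause of stopping this drug class. So the plan names withdrawal as the obstacle but does not list it as an outcome.

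A withdrawal after K has passed 5.5 is already reflected in the hyperkalemia rate. A withdrawal or cut made for potassium at or below 5.5 is not. In a single-arm, open-label study a low K >5.5 rate then has two explanations: potassium stayed controlled on the regimen, or spironolactone or the ACEi/ARB was cut before the threshold was reached. These lead to different conclusions under Aim 1, and the listed measures do not tell them apart.

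**Working it through.** **No planned figure to reproduce.** The plan gives no expected hyperkalemia rate, precision target or denominator for the potassium measures. Its one design calculation, 90% power with 20 subjects, concerns weight loss and has no bearing here.

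**Step 1: which responses to rising potassium remain open at or below 5.5?** Between 4.3 and 5.5 the protocol states no patiromer increase. The loop-diuretic dose is fixed and dietary potassium is set. What remains is to withhold the 200 mg step, stop spironolactone, or cut the ACEi/ARB. Entry is barred only from K 5.5 upwards (Item 5), so some patients may start close to the threshold.

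**Step 2: how do the listed measures score such a patient?** Take four hypothetical patients who all lose weight and never fall below 3.5.

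| Patient | K >5.5 | K <3.5 | Weight-based failure |
|---|---|---|---|
| A: K peaks at 5.2, both drugs continued | no | no | no |
| B: spironolactone stopped at K 5.2, K then stays in range | no | no | no |
| C: ACEi/ARB stopped at K 5.2, K then stays in range | no | no | no |
| D: K passes 5.5, spironolactone then stopped | yes | no | no |

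A, B and C are indistinguishable. Creatinine may also change, but it does not show that a drug was cut or why.

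**Step 3: how far could the picture differ?** The documents give neither a hyperkalemia rate nor a frequency of potassium-driven changes, so the counts below are assumptions. The number treated is not stated either. I use 20 and 30 (the target for completers) and 60 (planned enrollment), all from the Data Analysis Plan.

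The intervals are Clopper-Pearson 95%. For x patients out of n, the lower limit is the 0.025 quantile of Beta(x, n-x+1) and the upper limit is the 0.975 quantile of Beta(x+1, n-x). For x = 0 the lower limit is 0 and the upper limit is 1 - 0.025^(1/n).

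For example, 6/30 uses Beta(6, 25) and Beta(7, 24), giving 7.7% to 38.6%. For 0/30, 1 - 0.025^(1/30) = 11.6%.

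The serum rate is set at 10%. The other columns are further patients with a potassium-driven change at K at or below 5.5, shown as a separate proportion.

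| Treated | K >5.5 | No further changes | 10% changed | 20% changed | 30% changed |
|---|---|---|---|---|---|
| 20 | 2/20 (1.2-31.7%) | 0/20 (0-16.8%) | 2/20 (1.2-31.7%) | 4/20 (5.7-43.7%) | 6/20 (11.9-54.3%) |
| 30 | 3/30 (2.1-26.5%) | 0/30 (0-11.6%) | 3/30 (2.1-26.5%) | 6/30 (7.7-38.6%) | 9/30 (14.7-49.4%) |
| 60 | 6/60 (3.8-20.5%) | 0/60 (0-6.0%) | 6/60 (3.8-20.5%) | 12/60 (10.8-32.3%) | 18/60 (18.8-43.2%) |

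The K >5.5 column is the same in every scenario of a row. That follows from the definition of the measure and says nothing about which scenario is likely. The record can also favor the regimen: no changes among 30 treated patients would put the upper limit for their frequency at 11.6%, a result the present plan would not report.

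**The case against.** The strongest reply is that Aim 1 concerns safety, the serum rates answer it for the regimen as managed, and keeping spironolactone and ACEi/ARB on board is not a stated aim. Much of this stands. The serum rates are valid for what they measure, the plan does not contradict itself, and this is an exploratory pilot. But Item 4 makes withdrawal for potassium the central difficulty, so a reader will take a low rate as evidence that the difficulty was overcome. The rate alone does not carry that.

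Four stronger readings are tempting, and the documents do not support them.

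- **That staying at 100 mg is a safety failure, to be pooled with K >5.5.** Titration depends on response and labs, so remaining at 100 mg conforms to the protocol. Item 4 also cites increased natriuresis at 100 mg/day in 81% of patients resistant to high-dose loop diuretics. A composite would mix adherence to the protocol with an adverse laboratory finding.
- **That patients stopped early will drop out of the potassium rates.** Completers appear only in the recruitment target, not as an analysis set. Item 6 follows patients to euvolemia or discharge and does not tie follow-up to staying on drug. The denominator is unstated, which is worth fixing, but exclusion is not planned.
- **That drugs will often be cut below 5.5.** No rule directs it; the stated potassium response is patiromer. Discretion makes it possible, and its frequency is unknown.
- **That sizing of the next trial is compromised.** The only sizing calculation uses weight loss.

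**Conclusion.** The point holds as a limit on interpretation. The K >5.5 and K <3.5 incidences describe the managed regimen correctly. On their own, in one arm, they cannot show that potassium stayed controlled on that regimen, because a stop or cut for potassium at or below 5.5 is scored the same as uneventful treatment.

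The size cannot be estimated from the documents. Under the assumed 10% serum rate, anywhere from none to 30% of patients could have had such a change without altering the reported rate. The conclusion rests on two features of the text: physician discretion over spironolactone and ACEi/ARB without a potassium threshold, and no listed measure of those changes or their reasons. It does not rest on any assumed frequency. The correction is worth making because it changes what Aim 1 can conclude at little cost. It is not a reason to alter the treatment, the sample size or the primary measures.

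**What to change.** Keep the serum rates as primary safety measures, with the unit corrected to mEq/L and the denominator stated as all patients given at least one spironolactone dose. Then:

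1. Record, when the decision is made, the date, the K value and the reason for each hold, reduction or stop of spironolactone or of an ACEi/ARB.
2. In the same all-treated population, report beside the serum rates, as separate proportions with exact 95% CIs, the patients with a potassium-driven hold, reduction or stop of spironolactone, and those with a potassium-driven ACEi/ARB change. The recorded K shows how many were at or below 5.5. No composite is needed.
3. Report the spironolactone dose reached descriptively only, including non-titration to 200 mg where potassium is the recorded reason.

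The cost is one reason code per change, some inpatient chart abstraction and one added table. There are two drawbacks. Attribution to potassium is partly subjective in an open-label setting, and the safety picture may look less favorable. Showing the components separately next to the serum rates lets readers weigh both.

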
Insert response here
	
 1. Patients \geq 18 years old 2. Hospitalized with history of chronic heart failure and at least one symptom (dyspnea, orthopnea or edema) and one sign (rales, peripheral edema, ascites, or radiographic pulmonary edema or pleural effusion) 3. Women of child bearing age with negative urine pregnancy test 	
 1. Acute coronary syndrome 2. Patients with a baseline eGFR < 30 ml/min by MDRD equation 3. Baseline potassium concentration \geq 5.5 mEq/L 4. Requirement for intravenous vasodilators or inotropic agents 5. Systemic infection 6. Patients with concomitant end-stage liver disease 7. Hemodynamically significant uncorrected valvular disease

		
 8. Patients with pulmonary embolism 9. Patients with high output heart failure 10. Pregnant patients
Insert response here	Insert response here	Insert response here

Item 6

Research Plan / Description of the Research Methods *a. Provide a comprehensive narrative describing the research methods. Provide the plan for data analysis (include as applicable the sample size calculation).*

Step-by-Step Methods:

Pre-screening: Patients meeting the inclusion and exclusion criteria will be approached to participate in the study. Informed consent will be taken at this time. These patients will receive intravenous loop diuretic per the discretion of treating physician and will be closely followed for weight loss and symptoms relief.

Screening: The patients who don't respond as measured by symptoms relief or <0.5 kg weight loss/day

- a) Despite furosemide \geq 160 mg IV total daily dose or equivalent dose of torsemide or bumetanide. (1 mg bumetanide = 10 mg torsemide = 20 mg furosemide). OR
- b) After 48 hours irrespective of diuretic dose.

will be considered for the study intervention. Patients who have not participated in the pre-screening phase and do not respond adequately to furosemide >160 mg iv daily dose will directly be enrolled into active intervention part of the study.

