	
Data Analysis Plan: This is a pilot exploratory study to assess safety and efficacy of high dose spironolactone with patiromer to find the sample size for large randomized study. A previous study utilizing combination of loop diuretics and high dose spironolactone had generated mean weight loss of 4.49 ± 1.51 kg compared to 0.57 ± 1.14 kg¹⁶. Given that this weight loss seems inflated, a mean weight loss of 2 ± 1.3 kg with two-sided t-testing, and a significance level of 5%, provides a power of 90% with 20 subjects [PASS Version 08.0.8, NCSS, Kaysville Utah 2008]. Assuming that loop diuretics resistance will be seen in 50% of the patients and there will be some lost to FU during active intervention period, we propose to pre-screen at least 300 subjects to enroll 60 subjects with the goal to have at least 20-30 completers in active intervention arm.

Item 7 Risks Section: Complete the following table to describe the risks of all research procedures listed in Step 2, Institutional Form (items 28-34). Do not list risks of Routine care procedures here.	
 N/A, Risks are described in the informed consent document – do not complete this table.	
Research procedures example: 
 • History and physical • Questionnaire • Laboratory tests Add or delete rows as needed	Risks List the reasonably expected risks under the following categories as appropriate:
Insert procedure here	Serious and likely;  Insert risk here or enter "none" Serious and less likely;  Insert risk here or enter "none" Serious and rare;  Insert risk here or enter "none" Not serious and likely;  Insert risk here or enter "none" Not serious and less likely  Insert risk here or enter "none"
Insert procedure here	Serious and likely;  Insert risk here or enter "none" Serious and less likely;  Insert risk here or enter "none" Serious and rare;  Insert risk here or enter "none" Not serious and likely;  Insert risk here or enter "none" Not serious and less likely  Insert risk here or enter "none"

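### Do the accrual figures (300, 60, 20–30 completers) contradict the pre-screening definition, and does the unnamed denominator put the primary measures at risk?

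*Combined protocol and SAP*

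**What the plan says.** Item 6, Data Analysis Plan, sizes the weight-loss comparison so that it "provides a power of 90% with 20 subjects". It then sets the accrual target: "pre-screen at least 300 subjects to enroll 60 subjects with the goal to have at least 20-30 completers". Two assumptions support this. One has a rate: "Assuming that loop diuretics resistance will be seen in 50% of the patients". The other has none: "there will be some lost to FU during active intervention period".

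Item 6, Step-by-Step Methods, describes the flow. At pre-screening, eligible patients are approached, and "Informed consent will be taken at this time". Those who respond poorly to loop diuretic are then considered for the intervention. A second group skips pre-screening: poor responders on a high furosemide dose "will directly be enrolled into active intervention part of the study".

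The primary measures in Item 6 begin with "Incidence of hyperkalemia as defined by serum K" above 5.5, followed by hypokalemia, creatinine, weight loss and a breathlessness score. None carries a named analysis set. On follow-up, Item 6 says: "Patients will be followed till achievement of euvoolemia or discharge". It provides for daily weights and twice-daily serum chemistry. The Treatment Failures paragraph of the opening summary counts non-responders to spironolactone as failures and keeps them in the primary endpoint analysis.

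**The concern.** The Methods place consent at pre-screening and use *enrolled* for entry to the active intervention. Carried into the Data Analysis Plan, those meanings make 300 consented and 60 treated. The stated 50% then gives the wrong number at the first step, and the second step seems to accept that half or more of treated patients will not finish.

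That would matter for two reasons. Safety is the first primary aim, and its precision depends on how many patients are treated. And if many treated patients do not complete, the choice between all treated patients and completers could move both the hyperkalemia incidence and the mean weight loss. *Completer* is not defined, and there is no rule for missing weights.

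**Working it through.** **Inputs.** From Item 6, Data Analysis Plan: 300 pre-screened, 60 enrolled, at least 20–30 completers, 50% resistance, some loss (no rate), weight loss 2 kg with SD 1.3 kg, two-sided 5% level, 20 subjects for 90% power. The plan gives no consent rate, no dropout rate and no number of direct entries.

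**1. Where the 20 comes from.** A two-sample t-test with 10 per group has noncentrality 2 / (1.3 × √(1/10 + 1/10)) = 3.44 and power 90.2%, which reproduces the stated 90%. A one-sample test on 20 patients has noncentrality (2 / 1.3) × √20 = 6.88 and power above 99.9%; 7 patients already give 92.0%. Whether the two-group form suits a single-arm study is a separate question. Here it shows only that a test of mean weight change against zero does not depend on whether 20, 30 or 60 patients contribute, if the plan's 2 kg and 1.3 kg hold.

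**2. Accrual, reading A: 300 consented, 60 treated.**
- 300 × 0.50 = 150 candidates; 150 − 60 = 90 with no stated rate to remove them. The Methods do have a selection step here, since non-responders are only considered for the intervention.
- Non-completers: 60 − 30 = 30 (50.0%) or 60 − 20 = 40 (66.7%). The completer goal is a minimum, so these are upper bounds, not expected rates.

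**3. Accrual, reading B: 300 approached, 60 consented.**
- Implied consent rate: 60 / 300 = 20%, not stated in the plan.
- 60 × 0.50 = 30 treated, the top of the completer range.
- Non-completers: 30 − 30 = 0 (0%) up to 30 − 20 = 10 (33.3%).

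Reading B uses both stated assumptions in the order given and reaches the stated goal. It agrees with the Methods if the 300 are those approached, since not everyone approached consents. Direct entries would add to the treated count on either reading. They are already resistant, so the 50% does not apply to them.

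**4. Denominator, provisions side by side.**
- Non-responders stay in the primary endpoint analysis, so a responders-only efficacy result is excluded.
- Follow-up runs to euvolemia or discharge, in a sentence separate from the one on duration of treatment. Nothing ties the daily weights and chemistry to staying on spironolactone.
- No text restricts any analysis to completers. The word appears only in the sizing statement.

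**5. What the treated count does to safety precision.** With zero events, the exact two-sided 95% upper limit is 1 − 0.025^(1/n): 11.6% for n = 30 and 6.0% for n = 60. At an assumed 10% incidence (illustration only), the exact interval is 2.1–26.5% for 3/30 and 3.8–20.5% for 6/60. The limit for n = 20, 16.8%, would apply only to a completers-only analysis at the lower end of the goal, and the plan does not order one.

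**The case for a change.** The best case for a change is this. A pilot still reports incidences, and an incidence needs a denominator. If three hyperkalemia cases were seen (an assumed count), they would be 15% of 20, 10% of 30 or 5% of 60. The study is meant to size a larger randomized trial, so an unclear completion rate could carry forward. The rule on treatment failures covers non-responders only; it does not clearly place a patient who is losing weight when spironolactone is stopped before day 5, or one lost to follow-up. A short paragraph would settle all of this.

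Part of this stands. *Enroll* and *completer* are undefined, consent and dropout rates and direct-entry numbers are absent, and neither a safety set nor a missing-weight rule is written down. A tidy plan would have them.

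The rest does not carry the point to a required change. The Methods phrase is qualified, entry into the active part, so it does not fix what the plain *enroll* means in the sizing statement. The pilot will observe its own consent and completion numbers, and a later trial would use those rather than today's planning guess. Counting every treated patient for an incidence of harm is the ordinary default, and nothing in the plan points elsewhere. A mixed model on daily weights would be one reasonable choice, but for a small single-arm exploratory study it is a preference.

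**Conclusion.** The concern identifies missing detail, not an error. The accrual figures are consistent when 60 counts consented patients: 30 treated and at most 33% non-completion. This rests on an unstated 20% consent rate and leaves direct entries aside. The 50–67% figure is only an upper bound on the less natural reading.

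For the primary measures, the plan keeps treatment failures in and follows patients to euvolemia or discharge. No stated rule is shown to give a wrong result. The direction and size of any bias cannot be worked out from the documents and may be zero. What remains uncertain is whether about 30 or 60 patients will be treated, which moves the zero-event upper limit between 11.6% and 6.0%. The report will show the actual count. The verdict assumes that analysts take all treated patients as the base and report early stops and losses with their numbers, as is usual. On that footing no change to the plan is needed.
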